9.3. Sample Size Consideration

Assuming the primary endpoint response rate is 35%, 100 evaluable subjects will approximately yield 90% power to detect the lower bound of 95% confidence interval (calculated by Pearson-Klopper method) for primary endpoint response rate excludes 20%.

The study will enroll approximately 110 subjects by accounting for a 10% drop-out rate.

9.4. Background and Demographic Characteristics

9.4.1. Demographic and Baseline Characteristics

Standard demographic and baseline characteristics (including age and race), medical history, cancer diagnosis and prior anti-cancer therapy will be collected at screening as a baseline. Baseline efficacy variables and other prognostic variables will be assessed as well. The details of previous ruxolitinib treatment (eg, dose, best response, duration of response) will be summarized.

For quantitative variables, the summary using descriptive statistics will be provided, while frequency tabulations will be given for categorical variables.

9.4.2. Prior or Concomitant Medications

The prior and concomitant medications will be presented for the safety population.

Medications will be summarized according to the World Health Organization (WHO) drug dictionary, considering the first digit of the anatomical therapeutic chemical (ATC) class (anatomic category) and the first three digits of the ATC class (therapeutic category). All ATC codes corresponding to a medication will be summarized. Subjects will be counted for each of the ATC categories (anatomic or therapeutic) linked to the medication.

9.5. Subject Disposition

Subject disposition (analysis population allocation, entered, discontinued, along with primary reason for discontinuation) will be summarized using frequency and percentage for the study.

9.6. Efficacy Analysis

Unless otherwise specified, analysis of spleen volume response will be performed on the efficacy evaluable population, myelofibrosis symptom response analyses will be performed on the MFSAF population and spleen size response analyses will be performed on the safety population.

9.6.1. Spleen Volume Response Rate (RR) by MRI/CT:

Response rate of reduction in spleen volume is defined as proportion of subjects who have a \geq 35% reduction in spleen volume at the end of Cycle 6 as compared to baseline. The response rate and 95% confidence interval will be provided. In addition, a descriptive summary of spleen volumes measurements and percentage change from baseline will be provided. Subjects with a missing MRI/CT spleen volume at the end of Cycle 6 including those who meet the criteria for progression of splenomegaly before the end of Cycle 6 will be considered non-responders.

A sensitivity analysis will be conducted for response rate of subjects who have a $\geq 25\%$ reduction in spleen volume at the end of Cycle 6 as compared to baseline.

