Spleen volume will be assessed at the study site (MRI or CT Scan if MRI is contraindicated) during screening. The screening MRI/CT scan needs to be performed within 5 days before the start of treatment and after previous treatments have been discontinued for \geq 14 days according to exclusion criteria #9 and #10 (see Section 4.3). The locally assessed spleen volume will be recorded in the appropriate eCRF pages. The same method MRI or CT scan should be used consistently throughout the study. The MRI/CTs will be reviewed centrally.

- **Spleen size by palpation:**

Spleen size palpation in cm below left costal margin (LCM) will be assessed at the study site.

- **Eastern Cooperative Oncology Group (ECOG) performance status:**

Performance status will be assessed by the Investigator using the ECOG criteria provided in [Appendix J](#).

- **Symptoms response assessment:** Myelofibrosis Symptom Assessment Form (MFSAF) Refer to Section [6.7.1](#)

- **Progression of myelofibrosis to AML assessment:** Refer to Section [10.7](#)

Specified screening assessments must take place within 28 days after the date of the informed consent form signature. For subjects that are on ruxolitinib at the start of the screening period, the dose of ruxolitinib should be gradually tapered (refer to prescribing information) before the 14-day washout and supportive care provided to mitigate potential ruxolitinib withdrawal syndrome with close physician supervision. In some cases, restarting of ruxolitinib may be indicated and the subject should be screen failed. Future rescreening may occur after resolution of ruxolitinib withdrawal syndrome. In addition, for subjects that are on ruxolitinib at the start of the screening period or who have a laboratory abnormality detected during screening, the screening period may be extended to 35 days to allow for retesting to demonstrate resolution of the laboratory abnormality. In case a subject has a laboratory parameter related to an exclusion criterion that was under the influence of a treatment or medication (eg platelet transfusion in the last 7 days, G-CSF in last 14 days) retesting needs to be performed before enrollment after an appropriate washout period (refer to Section [4.3](#)).

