8.2. Prohibited Concomitant Medications

The following concomitant medications are specifically excluded during the course of the study:

- Cytotoxic, chemotherapeutic, targeted or investigational agents/therapies
- Immunomodulatory drug therapy (eg, thalidomide)
- Immunosuppressive therapy

- Systemic corticosteroids >10 mg/day prednisone or equivalent
- Hydroxyurea
- Interferon-alpha
- Anagrelide
- JAK inhibitors other than fedratinib
- Aspirin at doses of > 150 mg daily
- Any investigational agent

For information regarding clinically relevant P450 inducers, inhibitors, substrates, and Transporter Substrates refer to Section [8.3](#).

If a subject requires treatment with any new medications that are specifically excluded, the subject may need to be discontinued from treatment. The Investigator should consult the Medical Monitor regarding any questions about whether a new medication or dosage of existing medication would require the subject to discontinue from the study.

8.3. Clinically Relevant Cytochrome P450 Inducers, Inhibitors, Substrates, and Transporter Substrates

Fedratinib is metabolized by multiple cytochrome P450 enzymes (CYPs) in vitro, with prominent contribution from CYP3A4 and with a lesser contribution from CYP2C19.

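### Section 9.6.1 judges response on the end-of-Cycle-6 volume alone, so shrinkage after splenic irradiation or a prohibited spleen-active drug can count as a fedratinib response.

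*Combined protocol and SAP*

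**What the plan says.** **Response definition.** Protocol Section 9.6.1 opens: "Response rate of reduction in spleen volume is defined as proportion of subjects who have a" 35% or greater fall in spleen volume from baseline at the end of Cycle 6. Nothing in the definition refers to other treatment.

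**Forced non-response.** The same section makes these subjects non-responders: "Subjects with a missing MRI/CT spleen volume at the end of Cycle 6 including those who meet the criteria for progression of splenomegaly" ahead of that assessment. No other event is named. The single sensitivity analysis moves the threshold to 25%. The efficacy evaluable population (Section 9.2) asks for a baseline scan and at least one later scan, with no condition on other therapy.

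**Prohibited drugs.** Section 8.2 bars, among others, cytotoxic, targeted and investigational agents, hydroxyurea, interferon-alpha and JAK inhibitors other than fedratinib. On the consequence it says: "If a subject requires treatment with any new medications that are specifically excluded, the subject may need to be discontinued from treatment". Questions about continuing go to the Medical Monitor. No consequence for response status is given.

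**Splenectomy and irradiation.** Splenectomy appears as a prior-history exclusion (Section 4.3) and in footnotes to the response criteria in Appendix D. Splenic irradiation is not mentioned.

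**Baseline scan.** Section 6.1 requires that the screening scan "needs to be performed within 5 days before the start of treatment and after previous treatments have been discontinued for" at least 14 days, with reference to exclusion criteria 9 and 10.

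**Success criterion.** Section 9.3: "Assuming the primary endpoint response rate is 35%, 100 evaluable subjects will approximately yield 90% power" for the lower 95% limit to exclude 20%.

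**The concern.** The baseline volume is protected from other therapies by a 14-day washout tied to the scan itself. The end-of-Cycle-6 volume has no matching protection in the analysis. A percentage change between the two can then include the effect of something other than fedratinib.

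That a prohibited drug can produce the endpoint is shown by the protocol's own background. Section 1.1.2 reports a reduction of at least 35% in 41.9% of subjects on another JAK inhibitor against 0.7% on placebo. The population here has already been treated with that drug, so the figure shows that it is possible, not how likely it is.

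The trial has one arm, so no comparator shares the contamination. Crediting another therapy's shrinkage to fedratinib can only raise the reported rate. The claim is a fixed bar, and a few subjects can decide it when the observed rate lies close to that bar. The trial is also open-label, so without a written rule, decisions on individual responders could be made after their results are known.

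**Working it through.** **Inputs**
- n = 100 evaluable, planned rate 35%, rate to exclude 20%, stated power about 90% (Section 9.3).
- Interval: two-sided 95%, "calculated by Pearson-Klopper method", which I read as Clopper-Pearson.
- k = subjects per 100 who are responders only because of another spleen-directed therapy. The documents give no value. I assume k = 1 or 2, with k = 0 as reference.

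**Step 1. Success boundary.** The lower limit for x responders of 100 is the 2.5% quantile of Beta(x, 101 − x).
- x = 28: 19.48%, which does not exclude 20%.
- x = 29: 20.36%, which does.

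The claim therefore needs at least 29 responders.

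**Step 2. The plan's own figure.** Power = P(X ≥ 29) with X ~ Binomial(100, 0.35) = 91.5%. The stated figure of about 90% reproduces. The exact one-sided error at a true 20% is P(X ≥ 29 | 0.20) = 2.0%.

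**Step 3. Effect of contaminated responders.** If the rate from fedratinib alone is p, the rate under the current rule is p + k/100. The chance of meeting the claim is P(X ≥ 29) with X ~ Binomial(100, p + k/100).

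| Fedratinib-only rate p | k = 0 | k = 1 | k = 2 |
|---|---|---|---|
| 20% (rate to exclude) | 2.0% | 3.6% | 6.2% |
| 27% (near the boundary) | 36% | 45% | 54% |
| 35% (planned) | 91.5% | 94.3% | 96.3% |

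The 27% row is for illustration and is not a planning value. The model assumes that every contaminated subject would otherwise have been a non-responder. Where that is not so, the effect is smaller.

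**Step 4. Which events the text settles.**

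| Event before the end-of-Cycle-6 scan | Status under Section 9.6.1 |
|---|---|
| No scan at that time point | Non-responder |
| Progression of splenomegaly first | Non-responder |
| Prohibited spleen-active drug, stays on study, reduction ≥ 35% | Responder |
| Splenic irradiation, stays on study, reduction ≥ 35% | Responder |
| Splenectomy | Not settled: missing volume or zero volume |

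**The case against.** **Few subjects can follow this path.** Section 8.2 prohibits the drugs, Section 6 says that no waivers or deviations will be granted, and Section 11.1 lists protocol deviation as a reason to stop treatment. Under Table 3, footnote b, a subject who stops before Cycle 7 has the response assessments at the End of Treatment visit. One who stops well before the end of Cycle 6 would then ordinarily lack that scan and be a non-responder. If irradiation or surgery follows progression of splenomegaly, the existing rule already applies. All of this stands and limits the frequency. It does not close the path, because Section 8.2 leaves discontinuation open and Section 9.6.1 attaches no consequence.

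**Splenectomy.** A reader might infer that a removed spleen counts as a 100% reduction. The text does not support that reading over the other one: with no spleen to measure, the volume may be missing, which is non-response. What stands is that the plan does not say which.

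**The result is probably robust.** At the planned 35% the chance of success hardly moves, and any binomial threshold can turn on one subject. Both are correct. A reader might infer that the primary claim is unreliable or the sample size wrong; neither follows. The power reproduces, and no frequency of contamination is known.

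**A broad rule would err the other way.** Section 8.2 also lists systemic corticosteroids above 10 mg/day and immunosuppressants. Making every such use a failure would reclassify genuine responders given a short course for something unrelated. This stands and narrows the fix.

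**Detail is deferred.** Section 9.1 calls its content an overview and sends final methods to a SAP. That text is not among the material supplied and may contain the rule.

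**Conclusion.** The concern holds in a limited form. As written, Section 9.6.1 would count shrinkage after splenic irradiation or a prohibited spleen-active drug as a fedratinib response, and it leaves on-study splenectomy undefined. The gap is in the definition of what is estimated, not in the sample size. If the sponsor intends to count response whatever other therapy was given, that is a possible choice, but it should be stated, because it no longer measures the effect of fedratinib alone.

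The size is uncertain and probably small. With 1 or 2 such subjects per 100, the false-success chance at a true 20% goes from 2.0% to 3.6% or 6.2%, and success at 35% from 91.5% to 94.3% or 96.3%. The effect matters most near the boundary: 8 to 9 percentage points per subject at about 27%. These figures rest on an assumed frequency, on 100 evaluable subjects, and on each such subject being otherwise a non-responder. Settling the rule before results are known is worthwhile. If the separate SAP already has it, a reference to that text closes the point.

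**What to change.** Unless the separate SAP already does so, add to Section 9.6.1:

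*Subjects who undergo splenectomy or splenic irradiation, or who receive prohibited spleen-active or myelofibrosis-directed therapy (another JAK inhibitor, hydroxyurea, interferon-alpha, or a cytotoxic or other disease-directed agent), after the first dose and before the end-of-Cycle-6 scan are non-responders in the primary analysis. This does not apply automatically to aspirin, or to short courses of corticosteroid or immunosuppressant for an unrelated condition.*

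Then:
- report how many subjects the rule affects, by type of event;
- show the response rate without the rule as a sensitivity analysis;
- apply the same rule to the response rate by palpation (Section 9.6.2), which has the same omission.

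**Cost.** This is analysis wording only. Table 3 already collects concomitant medications and procedures until 30 days after the last dose, so no new data are needed. The sample size and the boundary of 29 in 100 do not change, and neither does the management of subjects. The reported rate may be slightly lower, and a subject already responding to fedratinib before such therapy would be counted as a non-responder. The sensitivity analysis makes that loss visible.

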9.6.2. Spleen Response Rate by Palpation (RRP)

Spleen response rate by palpation is the proportion of subjects with a spleen response according to the IWG-MRT 2013 ([Appendix D](#)) at the end of Cycle 6 as compared to baseline. This will be

calculated for subjects that have an enlarged spleen (≥ 5 cm below LCM) at baseline. Subjects with a missing spleen size assessment at the end of Cycle 6 including those who meet the criteria for progression of splenomegaly before the end of Cycle 6 will be considered not to be responders. The response rate and 95% confidence interval will be provided.

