9.6.5. Durability of Spleen Response by Palpation (DRP)

Durability of spleen response by palpation (DRP) is defined as time from the date of first documented palpable spleen response, according to the IWG-MRT 2013 (Appendix D) to the date of subsequent PD according to the IWG-MRT 2013 or death, whichever is earlier.

Durability of spleen response by palpation according to the IWG-MRT 2013 criteria will be calculated for subjects that have an enlarged spleen at baseline (≥ 5 cm below LCM), and that have a spleen response by palpation. In the absence of an event (ie, no loss of spleen response by palpation) before the analysis is performed, the DRP will be censored at the date of the last valid assessment performed before the analysis performed date.

Durability of spleen response by palpation will be analyzed using Kaplan-Meier (K-M) method. The K-M estimates of the 25th, 50th, and 75th percentiles and the 95% confidence interval of median will be provided, and K-M curves will be plotted.

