APPENDIX B. MYELOFIBROSIS SYMPTOM ASSESSMENT FORM (MFSAF) VERSION 4.0

Myelofibrosis Symptom Assessment Form version 4.0 7-Day Recall (MFSAF v4.0 7-Day Recall)

Instructions (to be modified based on data collection mode): The following questions refer to symptoms that you may experience as a result of your myelofibrosis. Please read through and complete the questions on the following screens. There are no right or wrong answers. Please select the answer that best applies to you.

Items:

1. During the past 7 days, how severe was your worst fatigue (weariness, tiredness)?

0	1	2	3	4	5	6	7	8	9	10
Absent						Worst Imaginable				

2. During the past 7 days, how severe were your worst night sweats (or feeling hot or flushed)?

0	1	2	3	4	5	6	7	8	9	10
Absent						Worst Imaginable				

3. During the past 7 days, how severe was your worst itching?

0	1	2	3	4	5	6	7	8	9	10
Absent						Worst Imaginable				

4. During the past 7 days, how severe was your worst abdominal discomfort (feeling pressure or bloating)?

0	1	2	3	4	5	6	7	8	9	10
Absent						Worst Imaginable				

5. During the past 7 days, how severe was the worst pain under your ribs on your left side?

0	1	2	3	4	5	6	7	8	9	10
Absent						Worst Imaginable				

6. During the past 7 days, what was the worst feeling of fullness you had after beginning to eat?

0	1	2	3	4	5	6	7	8	9	10
Absent						Worst Imaginable				

7. During the past 7 days, how severe was your worst bone pain (not joint or arthritis pain)?

0	1	2	3	4	5	6	7	8	9	10
Absent						Worst Imaginable				

**APPENDIX D. REVISED RESPONSE CRITERIA FOR
MYELOFIBROSIS: INTERNATIONAL WORKING
GROUP-MYELOPROLIFERATIVE NEOPLASMS
RESEARCH AND TREATMENT (IWG-MRT) AND
EUROPEAN LEUKEMIANET (ELN) CONSENSUS
REPORT (2013)**

Response categories	Required criteria (for all response categories, benefit must last for \geq 12 weeks to qualify as a response)
CR	Bone marrow: [*] Age-adjusted normocellularity; < 5% blasts; \leq grade 1 MF [†] and Peripheral blood: Hemoglobin \geq 100 g/L and $<$ UNL; neutrophil count \geq 1 \times 10 ⁹ /L and $<$ UNL; Platelet count \geq 100 \times 10 ⁹ /L and $<$ UNL; < 2% immature myeloid cells [‡] and Clinical: Resolution of disease symptoms; spleen and liver not palpable; no evidence of EMH

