PR	Peripheral blood: Hemoglobin \geq 100 g/L and $<$ UNL; neutrophil count \geq 1 \times 10 ⁹ /L and $<$ UNL; platelet count \geq 100 \times 10 ⁹ /L and $<$ UNL; < 2% immature myeloid cells [‡] and Clinical: Resolution of disease symptoms; spleen and liver not palpable; no evidence of EMH or Bone marrow: [*] Age-adjusted normocellularity; < 5% blasts; \leq grade 1 MF [†] , and peripheral blood: Hemoglobin \geq 85 but $<$ 100 g/L and $<$ UNL; neutrophil count \geq 1 \times 10 ⁹ /L and $<$ UNL; platelet count \geq 50, but $<$ 100 \times 10 ⁹ /L and $<$ UNL; < 2% immature myeloid cells [‡] and Clinical: Resolution of disease symptoms; spleen and liver not palpable; no evidence of EMH
Clinical improvement (CI)	The achievement of anemia, spleen or symptoms response without progressive disease or increase in severity of anemia, thrombocytopenia, or neutropenia [§]
Anemia response	Transfusion-independent patients: a \geq 20 g/L increase in hemoglobin level Transfusion-dependent patients: becoming transfusion-independent {
Spleen response	A baseline splenomegaly that is palpable at 5-10 cm, below the LCM, becomes not palpable** or A baseline splenomegaly that is palpable at $>$ 10 cm, below the LCM, decreases by \geq 50%** A baseline splenomegaly that is palpable at $<$ 5 cm, below the LCM, is not eligible for spleen response A spleen response requires confirmation by MRI or computed tomography showing \geq 35% spleen volume reduction
Symptoms response[#]	A \geq 50% reduction in the MPN-SAF TSS ^{††}
Progressive disease^{‡‡}	Appearance of a new splenomegaly that is palpable at least 5 cm below the LCM or A \geq 100% increase in palpable distance, below LCM, for baseline splenomegaly of 5-10 cm or A 50% increase in palpable distance, below LCM, for baseline splenomegaly of $>$ 10 cm or Leukemic transformation confirmed by a bone marrow blast count of \geq 20% or A peripheral blood blast content of \geq 20% associated with an absolute blast count of \geq 1 \times 10 ⁹ /L that lasts for at least 2 weeks
Stable disease	Belonging to none of the above listed response categories
Relapse	No longer meeting criteria for at least CI after achieving CR, PR, or CI, or Loss of anemia response persisting for at least 1 month or Loss of spleen response persisting for at least 1 month

EMH, extramedullary hematopoiesis (no evidence of EMH implies the absence of pathology- or imaging study-proven non-hepatosplenic EMH); LCM, left costal margin; UNL, upper normal limit.

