* Baseline and posttreatment bone marrow slides are to be interpreted at one sitting by a central review process. Cytogenetic and molecular responses are not required for CR assignment.

† Grading of MF is according to the European classification

Thiele et al. European consensus on grading bone marrow fibrosis and assessment of cellularity. *Haematologica*. 2005;90:1128.

‡ Immature myeloid cells constitute blasts + promyelocytes + myelocytes + metamyelocytes + nucleated red blood cells. In splenectomized patients, < 5% immature myeloid cells is allowed.

§ Increase in severity of anemia constitutes the occurrence of new transfusion dependency or a ≥ 20 g/L decrease in hemoglobin level from pretreatment baseline that lasts for at least 12 weeks. Increase in severity of thrombocytopenia or neutropenia is defined as a 2-grade decline, from pretreatment baseline, in platelet count or absolute neutrophil count, according to the CTCAE version 4.0. In addition, assignment to CI requires a minimum platelet count of $\geq 25\,000 \times 10^9/L$ and absolute neutrophil count of $\geq 0.5 \times 10^9/L$.

|| Applicable only to patients with baseline hemoglobin of < 100 g/L. In patients not meeting the strict criteria for transfusion dependency at the time of study enrollment, but have received transfusions within the previous month, the pretransfusion hemoglobin level should be used as the baseline.

{ Transfusion dependency before study enrollment is defined as transfusions of at least 6 units of packed red blood cells (PRBC), in the 12 weeks prior to study enrollment, for a hemoglobin level of < 85 g/L, in the absence of bleeding or treatment-induced anemia. In addition, the most recent transfusion episode must have occurred in the 28 days prior to study enrollment. Response in transfusion-dependent patients requires absence of any PRBC transfusions during any consecutive “rolling” 12-week interval during the treatment phase, capped by a hemoglobin level of ≥ 85 g/L.

In splenectomized patients, palpable hepatomegaly is substituted with the same measurement strategy.

** Spleen or liver responses must be confirmed by imaging studies where a $\geq 35\%$ reduction in spleen volume, as assessed by MRI or CT, is required. Furthermore, a $\geq 35\%$ volume reduction in the spleen or liver, by MRI or CT, constitutes a response regardless of what is reported with physical examination.

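### Under Section 9.6.2 as written, change on palpation cannot decide who is a palpation responder: Appendix D leaves that to the 35% MRI/CT volume reduction, in conflict with Table 2.

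*Combined protocol and SAP*

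**What the plan says.** Section 9.6.2 defines the endpoint by reference: "Spleen response rate by palpation is the proportion of subjects with a spleen response according to the IWG-MRT 2013", as set out in Appendix D, at the end of Cycle 6 against baseline. It is "calculated for subjects that have an enlarged spleen", meaning at least 5 cm below the left costal margin. A missing spleen size at that visit counts as non-response. No clause of Appendix D is exempted.

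Appendix D has four relevant clauses:
- The spleen response row gives palpation limbs (a 5 to 10 cm spleen becomes impalpable; a larger one shrinks by at least half) and adds: "A spleen response requires confirmation by MRI or computed tomography showing" a volume reduction of at least 35%.
- Footnote ** repeats the requirement: "Spleen or liver responses must be confirmed by imaging studies where" that reduction is seen.
- The same footnote says that a reduction of this size "constitutes a response regardless of what is reported with physical examination".
- The header row adds a duration condition, "for all response categories, benefit must last for" at least 12 weeks.

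Section 9.6.5 starts the durability clock (DRP) at the "first documented palpable spleen response, according to the IWG-MRT 2013".

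Table 2 defines RRP differently: a fall of at least 50% in palpated spleen size, with no imaging condition. Table 1 lists palpated spleen reduction as a secondary objective of its own.

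**The concern.** A rule that makes imaging both required and sufficient leaves the palpation limb with nothing to decide. A subject whose 12 cm spleen becomes impalpable with a 33% volume reduction would be a non-responder by palpation. A subject whose 12 cm spleen feels unchanged with a 36% reduction would be a responder by palpation.

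The palpation objective would then not be measured by the endpoint that carries its name. RRP would be reported with its own 95% confidence interval and would look like support from a second kind of measurement, when most of its agreement with the primary endpoint is built in. A programmer following Table 2 and one following Section 9.6.2 could also classify the same subject differently.

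**Working it through.** **The plan's own figure.** No sample size or power is given for RRP. The only planning figure is for the primary endpoint (Section 9.3): about 90% power, true rate 35%, 100 evaluable subjects, lower 95% limit above 20%. With an exact interval, taken as two-sided, the smallest qualifying count is 29 of 100 (lower limit 20.36%; 28 of 100 gives 19.48%). The probability of 29 or more at a true rate of 35% is 91.5%, so the figure reproduces. It is used below only as a source of illustrative inputs.

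**Step 1: the response rule.** Let P mean that the palpation criterion is met and S that MRI/CT shows a reduction of at least 35%. The confirmation clauses give P and S; the override in footnote ** adds S alone. Response = (P and S) or S = S.

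| P | S | Appendix D response | Table 2 response (palpation only) |
|---|---|---|---|
| no | no | no | no |
| no | yes | yes | no |
| yes | no | no | yes |
| yes | yes | yes | yes |

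The Appendix D column equals S in four of four rows. The Table 2 column differs from it in both discordant rows.

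**Step 2: what still separates RRP from the primary endpoint.**
- Population: Section 9.6 puts spleen size response in the safety population and spleen volume response in the efficacy evaluable population.
- Baseline: RRP needs at least 5 cm below the costal margin. Inclusion criterion 5 also admits subjects on volume alone.
- Missing data: a missing palpation at Cycle 6 is non-response for RRP. Section 9.6.2 has no rule for a missing confirmatory scan.
- Duration: Appendix D asks for 12 weeks; the primary endpoint does not.

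To show the possible size, assume 35 imaging responders among 100 imaging-evaluable subjects, 110 treated, all with a baseline spleen of at least 5 cm. Let q be the share of responses that last 12 weeks and m the share with palpation missing. The values of q and m are assumptions.

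RRP = 35 × q × (1 − m) / 110

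| q | m | RRP |
|---|---|---|
| 1 | 0 | 35/110 = 31.8% |
| 0.9 | 0 | 31.5/110 = 28.6% |
| 0.8 | 0 | 28/110 = 25.5% |
| 0.9 | 0.05 | 29.925/110 = 27.2% |
| 0.8 | 0.05 | 26.6/110 = 24.2% |

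The corresponding primary rate is 35/100 = 35%. The rates differ, but none of the gap comes from change in palpated size.

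**Step 3: the 12-week clause.** End of Cycle 3 to end of Cycle 6 is 3 × 28 = 84 days, which is 12 × 7. For a response first imaged at the end of Cycle 6, the next scheduled on-treatment scan is at the end of Cycle 12, 6 × 28 = 168 days later. Section 9.6.2 does not say whether the clause applies to an assessment at one time point.

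**Step 4: the palpation threshold.** Even without the imaging clauses, Table 2 and Appendix D differ for 5 to 10 cm spleens. A fall from 8 cm to 3 cm is (8 − 3)/8 = 62.5%: a response under Table 2, but not under the Appendix D limb, because the spleen is still palpable. A fix therefore has to name the threshold.

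**The case against.** The strongest reply is that a palpation-only endpoint was plainly meant. The protocol tends to say spleen volume for imaging and spleen size for palpation. The missing-data rule in Section 9.6.2 turns on spleen size, Section 9.6.5 speaks of response by palpation, and Appendix D has explicit palpation limbs. On this view Section 9.6.2 merely fails to say that the imaging clauses are set aside, and keeping Table 2 cures the problem. RRP also has no hypothesis test or power claim, and Section 9.1 leaves final methods to the SAP; the text reviewed contains no separate SAP wording on RRP.

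Much of this stands. Keeping the Table 2 definition does remove the fault, so the point belongs with reconciling the two definitions. The evidence of intent is good, but it makes the literal rule more clearly a mistake; it does not change what the rule says.

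Some stronger readings are tempting but unsupported:
- A reader might infer that RRP simply repeats the primary endpoint, with complete concordance. Population, baseline size, missing data and, if enforced, the 12-week clause separate them.
- A reader might infer that palpation data go unused. Palpation sets the denominator and the missing-data rule, and palpable growth enters the Appendix D progression criteria, subject to imaging confirmation.
- A reader might infer that a response can be dated only at a scan, or that 12 weeks can be shown only by two scans. Appendix D says neither. Scans also continue at Cycles 18 and 24, at end of treatment and every sixth cycle afterwards (Section 6.5).

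**Conclusion.** The point holds in a limited form. Under Section 9.6.2 with Appendix D read literally, change on palpation has no influence on who is an RRP responder. RRP is then a restricted, possibly stricter, version of the 35% volume response, and its agreement with the primary endpoint is largely built in. This conflicts with the palpation objective and with Table 2. The start of DRP inherits the fault.

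The logical result needs no numerical assumption beyond applying every Appendix D clause as written. The rates of 24.2% to 31.8% are illustrations only. The documents give no frequency of disagreement between palpation and imaging, so the number of subjects who would change category is unknown. The primary analysis is unaffected. The correction should be made before RRP and DRP are programmed.

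**What to change.** Reconcile Sections 9.6.2 and 9.6.5 with Table 2:
- Score RRP, and the response that starts DRP, on palpation alone: centimetres below the left costal margin, a fall of at least 50% from baseline, in subjects with a baseline of at least 5 cm.
- State that three Appendix D clauses do not apply to RRP or to the start of DRP: imaging confirmation, the imaging override in footnote **, and the 12-week duration.
- Report the MRI/CT-confirmed IWG-MRT response separately, in a palpation-by-imaging table, so that agreement is observed and not assumed.

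The cost is a few sentences and one table; palpation and scans are already collected. The downside is that RRP can no longer be labelled a full IWG-MRT 2013 spleen response. The separate table keeps the confirmed response available for readers who want it.
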